12.5	AOM Treatment Failure	25
12.6	AOM Relapse	
12.7	AOM Recurrence	26
13.	STATISTICAL METHODS	27
13.1	Logistic Regression	27
13.2	GLM	27
13.3	Missing Observations	27
13.4	Multiplicity	27
14.	SAFETY MONITORING COMMITTEE	28
15.	SEQUENCE OF PLANNED ANALYSES	28
15.1	Final Analysis	28
16.	CHANGES FROM THE PROTOCOL	28
REFI	ERENCES	29
APPF	ENDIX A: SCHEDULE OF ACTIVITIES	30

APPENDIX B: TABLES OF CONTENTS FOR TABLES, FIGURES, AND LISTINGS...32

Confidential Page 7 of 35

LIST OF ABBREVIATIONS

ABBREVIATION
AE adverse event
AOM acute otitis media

AOM-SOS Acute Otitis Media Severity of Symptom

ATC Anatomical-Therapeutic-Chemical

BID twice per day
BMI body mass index
CSR Clinical Study Report
eCRF electronic case report form

EOS end of study

GLM general linear model

ICH International Conference on Harmonisation

LS least squares

MedDRA Medical Dictionary for Regulatory Activities

MEE middle ear effusion mITT modified intent-to-treat

N/A not applicable

OME otitis media with effusion OP0201 OP0201 nasal aerosol

pMDI pressurized metered dose inhaler

PP per protocol PT Preferred Term

SAP Statistical Analysis Plan SD standard deviation

SE standard error

SMC Safety Monitoring Committee

SOC System Organ Class

TEAE treatment-emergent adverse event

TESAE treatment-emergent serious adverse event

TFLs tables, figures, and listings
TM tympanic membrane

WHO-DD World Health Organization Drug Dictionary

Confidential Page 8 of 35

PREFACE

The purpose of this statistical analysis plan (SAP) is to outline the planned analyses and reporting to support the completion of the Clinical Study Report (CSR) for Novus Therapeutics Protocol OP0201-C-006. The planned analyses identified in this SAP will be included in regulatory submissions and/or future manuscripts. Also, exploratory analyses not necessarily identified in this SAP may be performed to support the clinical development program. Any posthoc, or unplanned, analyses not identified in this SAP will be clearly identified in the CSR.

The structure and content of this SAP provides sufficient detail to meet the requirements identified by the United States of America Food and Drug Administration and International Conference on Harmonisation (ICH) of Technical Requirements for Registration of Pharmaceuticals for Human Use: Guidance on Statistical Principles in Clinical Trials. All work planned and reported for this SAP will follow internationally accepted guidelines published by the American Statistical Association for statistical practice.

The following documents were also considered in preparation for writing this SAP:

- Clinical Research Protocol OP0201-C-006, Amendment 3 (21 August 2019)
- ICH E3 Guideline: Structure and Content of Clinical Study Reports³
- ICH E6 Guideline on Good Clinical Practice⁴
- ICH E8 General Considerations for Clinical Trials⁵
- ICH E9 Statistical Principles for Clinical Trials⁶
- Statistical Analysis Plans: Principles and Practice⁷

The SAP is a supplement to the study protocol, which should be referred to for additional details on study design, study conduct, and other operational aspects of the study.

Confidential Page 9 of 35

1. BACKGROUND

It has been established that most young children with acute otitis media (AOM) will have persistent middle ear effusion (MEE) or otitis media with effusion (OME) 2 to 3 weeks after AOM diagnosis, despite treatment with oral antibiotics. Bulging tympanic membrane (TM) and recent onset of acute symptoms are the main findings that clinicians use to discriminate AOM from OME. The purpose of this study is to develop a better understanding of the safety, tolerability, and efficacy of intranasal OP0201 as an adjunct treatment to oral antibiotics for AOM in infants and children, and to assist in the design of future clinical trials.

2. STUDY OBJECTIVES

2.1 Primary Objectives

The primary objectives of the study are to evaluate the safety, tolerability, and efficacy of intranasal OP0201 compared with placebo in accelerating AOM resolution by reducing and/or eliminating MEE in infants and children when given as an adjunct treatment to oral antibiotics as assessed using pneumatic otoscopy.

2.2 Secondary Objectives

The secondary objectives of the study are to evaluate the efficacy of intranasal OP0201 compared with placebo in accelerating and maintaining AOM resolution, and reducing the likelihood of MEE (OME) in infants and children when given as an adjunct treatment to oral antibiotics as assessed using other measures (ie, tympanometry, Acute Otitis Media Severity of Symptom (AOM-SOS) score, and AOM recurrence and AOM relapse rates).

2.3 Other Objective

Another objective of this study is to obtain feedback from parents/caregivers on the pressurized metered dose inhaler (pMDI) device to optimize design of the device for pivotal studies.

3. STUDY DESIGN

This is a Phase 2a, single-center, double-blind, randomized, placebo-controlled, parallel-group study to assess the safety, tolerability, and efficacy of 20 mg per day intranasal OP0201 (10 mg administered twice/day (BID) over 10 days for a total of 20 doses) as an adjunct therapy to oral antibiotic treatment of AOM in infants and children aged 6 to 24 months (inclusive). Subjects will be followed for up to 20 days after study treatment is discontinued. The total duration of study participation for each subject is up to 30 days, which includes 4 clinic visits. An unscheduled interim/sick visit may occur for safety purposes or if AOM symptoms have relapsed or worsened. The Schedule of Activities is in Appendix A.

4. TREATMENT GROUPS AND STUDY ENDPOINTS

4.1 Treatment Group Comparisons

The treatment groups to be compared are OP0201 and placebo.

Confidential Page 10 of 35

4.2 Study Endpoints

4.2.1 Safety Endpoints

- Incidence, seriousness, severity, and relationship to IP of treatment-emergent adverse events (TEAEs)
- Shifts from baseline (normal, abnormal) in vital signs (temperature, respiratory rate and pulse)
- Shifts from baseline (normal, abnormal) in physical examination, including visual examination of the nasopharynx and oropharynx
- Shifts from baseline in examination of the TM (via otoscopy and endoscopy)

4.2.2 Primary Efficacy Endpoint Family

The primary efficacy endpoint family is comprised of the following endpoints:

- No bulging of the TM assessed at the Day 4 visit by pneumatic otoscopy
- No MEE (OME) assessed at the Day 12 visit by pneumatic otoscopy

4.2.3 Secondary Efficacy Endpoints

Secondary efficacy endpoints are:

- No MEE assessed at the Day 4 and Day 28 visits by pneumatic otoscopy
- No bulging of the TM assessed at the Day 12 and Day 28 visits by pneumatic otoscopy
- Normal tympanogram (Type A) assessed at the Day 4, Day 12, and Day 28 visits by tympanometry
- Complete or near complete resolution of symptoms (AOM cure), defined as an AOM-SOS score ≤ 2, assessed at the Day 4 Visit, the Day 12 Visit and the Day 28 Visit.
- Change from baseline in the AOM-SOS score over the 10-day planned treatment period by parent/caregiver diary data
- At least a 50% reduction from baseline in the in-clinic AOM-SOS score, assessed at the Day 4, Day 12, and Day 28 visits
- AOM treatment failure (clinical failure) at the Day 12 Visit, with treatment failure defined as moderate to severe bulging of the TM, or mild bulging of TM with recent (less than 48 hours) onset of ear pain (otalgia), or mild bulging of the TM with intense erythema of the TM.
- AOM relapse defined as those with clinical success at the Day 12 visit and who return for an interim/sick visit before Day 17 and have AOM. Clinical success is defined as no moderate to severe bulging of the TM, and no mild bulging of the TM with recent (less than 48 hours) onset of ear pain (otalgia), and no mild bulging of the TM with intense erythema of the TM.
- AOM recurrence defined as clinical success at the Day 12 visit and return for an interim/sick visit from Day 17 through Day 28 and have AOM. Clinical success is defined as no moderate to severe bulging of the TM, and no mild bulging of the TM with recent (less than 48 hours) onset of ear pain (otalgia), and no mild bulging of the TM with intense erythema of the TM.

Confidential Page 11 of 35

4.2.4 Other Endpoints

• Parent/caregiver's input on device experience on Day 12.

5. SAMPLE SIZE AND POWER

The power calculation is based on a 2-sided Pearson chi square test of each of the two endpoints in the primary efficacy endpoint family and control of type 1 error using the step-up Hochberg procedure.⁸ The minimally important difference in proportions for both endpoints is approximately 0.25. With 70 subjects randomized per treatment group, an assumed dropout rate of 10%, and using multiple imputation as described in Section 13.3, this study will have 93% power to detect a treatment effect in at least one of the two endpoints assuming 40% of placebotreated subjects will have no bulging TM at Day 4 and 30% of placebotreated subjects will have no MEE at Day 12. A summary of sample size requirements is as follows:

Total N	Power
100	82%
102	82%
120	88%
132	91%
140	93%

6. TREATMENT ASSIGNMENT, BLINDING, AND UNBLINDING

6.1 Treatment Assignment

Following Screening, but before any treatment-related procedures, eligible subjects will be randomly assigned in a 1:1 ratio to either OP0201or placebo. The randomization schedule will be generated by the University of Pittsburgh Statistics Department. Randomization will be stratified by daycare attendance (yes, no) and age (≥ 6 to <12 months, ≥ 12 to ≤ 24 months). Daycare attendance will be defined as exposure to 3 or more children outside of the home for 10 or more hours per week. A fixed block size of 4 will be used.

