### Number of Investigators and Study Centers:

One Principal Investigator at 1 study center along with up to 4 satellite sites in the US are expected to participate in this study.

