### **8.3 Other Assessments**

1. Otalgia (per Investigator judgment in consultation with parent/caregiver): yes, no. Information used by the Investigator to confirm diagnosis. Data will be collected in the eCRF and summarized.
2. Endoscopic examination with image capture of each ear when possible, using an endoscope iPhone application (Pitt CMU iTM). Information used by the Investigator to confirm agreement of findings with Sub-investigators. Data will not be collected in the eCRF or analyzed.
3. Parent/caregiver's input on Device Experience Questionnaire. Data will be collected in the eCRF and summarized in data listings.

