13. STATISTICAL METHODS

13.1 Logistic Regression

Logistic regression models will include treatment group as a main effect and the randomization stratifiers (age group, daycare attendance) and an appropriate baseline value (if applicable) as covariates. Model-based LS means and SEs will be reported for each treatment group, along with a p-value for the treatment group comparison. For sparse data, two-sided Fisher's exact tests will be used (ie, with no covariate adjustment).

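### Site is recorded and tabulated for both primary endpoints but is left out of the SAP 13.1 models; pre-specifying one main-versus-satellite term would cost almost nothing and could recover a little power

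*SAP*

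**What the plan says.** SAP 3 describes the trial this way: "This is a Phase 2a, single-center, double-blind, randomized, placebo-controlled, parallel-group study". The synopsis in Protocol 1.1 uses the same label for the design, but under the number of centers it expects "One Principal Investigator at 1 study center along with up to 4 satellite sites in the US", so up to five locations.

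For allocation, SAP 6.1 says "Randomization will be stratified by daycare attendance (yes, no) and age" and "A fixed block size of 4 will be used". For the primary analysis, SAP 13.1 puts treatment in the logistic model with "the randomization stratifiers (age group, daycare attendance) and an appropriate baseline value (if applicable) as covariates". Site is in neither list.

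Site does appear elsewhere in the SAP. It is a subgroup for summaries of the primary endpoint family (8.4), a baseline characteristic (9.6) and an identifier in the listings (8.2). Appendix B gives it a table for each primary endpoint (14.2.1.11.1 and 14.2.2.11.1). All of these uses are descriptive.

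Both primary endpoints, no bulging at Day 4 and no effusion at Day 12, are read by pneumatic otoscopy (SAP 4.2.2). Protocol 8.1 requires otoscopists who have completed a common training program. Protocol 8.3 adds endoscope images: "Information used by the Investigator to confirm agreement of findings with Sub-investigators". The images are neither entered in the eCRF nor analyzed.

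**The concern.** Otoscopy is a visual judgement, and children seen at satellites may differ from those at the main center. If response rates differ by site, a model without site ignores a known baseline predictor. In logistic regression, leaving out a balanced prognostic covariate pulls the estimated log odds ratio toward zero, and some power is lost.

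The second issue is pre-specification. The sponsor will see both primary endpoints tabulated by site. If rates differ and the arms happen to be unevenly spread over sites, the obvious question is whether the result survives adjustment. The SAP names no such analysis, so under its Preface one run later would have to be labelled post hoc. With decisions made at 0.05 or 0.025, that answer would carry less weight than one planned in advance.

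**Working it through.** **Inputs from the documents.** SAP 5: 70 randomized per arm, 10% dropout, response 40% vs 65% at Day 4 and 30% vs 55% at Day 12 (placebo rate plus 0.25), stated power 93%. SAP 13.4: Hochberg at 0.05/0.025. Informative children per arm: 70 × 0.90 = 63 (ignoring the three children excluded in SAP 7).

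**Assumed, because the documents do not say.** Satellite share 10% to 40%; main-versus-satellite difference in response of 0, 15, 25 or 35 points.

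**Step 1: reproduce the SAP's 93%.** For one endpoint, power = Φ[(0.25 − z·SE0)/SE1], with SE0 = √(2·p̄(1−p̄)/63) and SE1 = √([p1(1−p1)+p2(1−p2)]/63).

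- Day 4: p̄ = 0.525, SE0 = 0.0890, SE1 = 0.0861. Power is 81.0% at 0.05 and 72.1% at 0.025.
- Day 12: p̄ = 0.425, SE0 = 0.0881, SE1 = 0.0852. Power is 81.8% at 0.05 and 73.1% at 0.025.
- Hochberg, endpoints independent: at least one p ≤ 0.025 has probability 1 − (0.279 × 0.269) = 92.5%. Both p-values between 0.025 and 0.05 adds (0.810 − 0.721)(0.818 − 0.731) = 0.8%. The total is 93.3% (93.4% by simulation).

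The stated 93% is reproduced. It assumes independence; with a correlation of 0.3 it would be 89.9%.

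**Step 2: does leaving site out harm validity?** Site is fixed before treatment and allocation ignores it, so the imbalance between arms has mean zero. With satellite share s, the arm difference in share has SD √(2s(1−s)/63): 0.071 at s = 0.20 and 0.087 at s = 0.40. A 25-point site difference turns that into a shift in the Day 4 difference with SD 0.25 × 0.071 = 0.018 to 0.25 × 0.087 = 0.022. The sampling SE is 0.086, and the ordinary SE already covers this variation. Simulated familywise error without site was 5.0% to 5.3%, with or without between-site variation.

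**Step 3: add one two-level term.** Simulation with 63 per arm, both endpoints, Hochberg, and models with and without main center vs pooled satellites:

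| Assumed site difference | Change in power for at least one endpoint, shares 10–40% |
|---|---|
| 0 points | about −0.1 to 0 points |
| 15 points | +0.4 to 0.7 |
| 25 points | +0.8 to 2.2 |
| 35 points | +1.5 to 3.8 |

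Familywise error was 4.7% to 5.0% either way. A second simulation restricted to shares of 20% and 40% gave gains of 0.3–0.6, 1.5–2.3 and 2.6–4.1 points, so the upper ends agree within 0.3 points.

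**Step 4: why pool the satellites?** With four separate site indicators the model lost 0.4 to 0.9 points of power when sites did not differ, and null error was 5.2% to 6.0%. The pooled term avoids both costs.

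**The case against.** Much of the case for leaving the plan alone stands.

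- **The SAP does not ignore site.** It describes site in four places. The single-center label repeats the protocol's own wording for one Principal Investigator with satellites. That part is a matter of wording.
- **A reader might infer bias or an inflated error rate.** The documents do not support that. Given an imbalance of 10 to 20 points and a 25-point site difference, the error rate at the 0.05 level would be about 6% to 9%. That is conditional on an unlucky draw: with satellite shares of 20% to 50%, the 20-point imbalance behind the upper end occurs in only about 0.5% to 2.4% of trials. Averaged over all draws, the test holds its level.
- **A reader might infer that randomization should have been stratified by site.** Four existing strata times five sites is 20 strata, or 140/20 = 7 children each with blocks of 4. Enrollment was also already under way at Amendment 3. Stratifying by daycare and age alone is defensible.
- **Site is not otoscopist.** Nothing says assessors follow site, training is common to all, and the image check is a safeguard, not evidence of disagreement. Absent tympanometry at satellites has no bearing on otoscopic endpoints.
- **Case mix is partly covered** for bulging, since Protocol 9.4.1 names baseline degree of bulging as a covariate and SAP 13.1 allows a baseline value.
- **The gain is small** unless sites differ widely, and this is an exploratory Phase 2a trial.

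None of this is a reason to omit a recorded baseline variable that costs about 0.1 point of power at worst, or to leave the adjusted analysis unplanned.

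**Conclusion.** The point holds as a minor improvement. The primary test is valid as written. What the plan gives up is a little power: roughly half a point if sites differ by 15 points, about 1 to 2 points at 25, and up to about 4 at 35. It also gives up the chance to report a site-adjusted result as planned. These sizes rest on assumed satellite shares and site differences, on the SAP's response rates and on independent endpoints. If nearly all children come from the main center, or sites do not differ, there is nothing to gain and almost nothing to lose. The wording mismatch between the single-center label and the satellite sites is certain from the text.

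**What to change.** Before unblinding:

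1. In SAP 13.1, add one two-level site covariate (main center vs satellites pooled) to the logistic models for both primary endpoints. If the sponsor prefers to keep the primary model, name the same adjusted model as a pre-specified sensitivity analysis for both endpoints.
2. Fix in advance, on blinded enrolment counts, the rule for omitting the term if the satellites contribute too few children to estimate it.
3. In SAP 3, reword the design description so that it agrees with the satellite sites in Protocol 1.1.

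Leave randomization as it is. The cost is a few sentences and one model parameter, with no new data. The term removes otoscopist differences only as far as otoscopists follow site, and pooling leaves differences among the satellites unadjusted.

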6.2 Blinding

OP0201 and placebo will be identical in physical appearance. The specific treatment each subject will receive (OP0201 or placebo) will not be disclosed to the Investigator, study center staff, subject, Sponsor, study vendors, or the Safety Monitoring Committee (SMC). The treatment codes will be held by the University of Pittsburgh Statistics Department.

7. ANALYSIS POPULATIONS

Screened Population: Subjects whose parent/legal guardian signed the informed consent form.

Confidential Page 12 of 35

Safety Population: Subjects who received at least one intranasal spray of study treatment. Subjects will be summarized and analyzed based on treatment received.

Modified Intent to treat (mITT) Population: Subjects who were randomized excluding the first 3 subjects dosed (subject numbers 1001, 1002 and 1003), as there was a known device malfunction for these subjects. Subjects will be summarized and analyzed based on randomization assignment, regardless of treatment received.

Per Protocol (PP) Population: Subset of the mITT population with no protocol violations that may have affected the primary efficacy endpoint family.

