## 9.3 Populations for Analyses

Four populations will be considered. The screened population will be all Participants whose parent/legal guardian signs the ICF. Safety data and secondary efficacy endpoints will be analyzed using the safety population defined as all Participants who received at least 1 intranasal spray of study treatment. The intent-to-treat (ITT) population is defined as all randomized Participants and will be used to assess the primary efficacy endpoint family. The per-protocol population is defined as the subset of the ITT population who have no protocol violations affecting the primary efficacy endpoint family and will be used to confirm results from the primary efficacy endpoint family.

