12. EFFICACY PARAMETERS

Efficacy parameters will be listed for the mITT population. For the family of primary efficacy endpoints, summaries and analyses will be done using the mITT population unless otherwise noted. For secondary efficacy endpoints, complete-cases analyses will be done using the mITT population, whereby for each endpoint only subjects with complete data are included. Results from statistical analyses of treatment group differences in secondary endpoints may be reported to aid in interpretation and to assist in the design of future clinical trials.

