12.1 Bulging TM

The presence/absence of bulging TM will be evaluated as part of the ear examination (see Section 11.4) done at each study visit; each ear will be evaluated separately.

A listing of bulging TM will be produced separately from the listing of ear examination parameters noted in Section 11.4.

Endpoints

The definition of bulging TM will be presence of 1+, 2+, or 3+ bulging on ear examination. Note: at least mild bulging is an inclusion criterion.

No bulging TM at the Day 4 visit is one of two endpoints in the primary efficacy endpoint family (see Section 13.5). The hypothesis set to be tested is:

Confidential Page 22 of 35

$$\begin{aligned} &H_o \colon P_A = P_P \\ &vs. \\ &H_A \colon P_A \neq P_P \end{aligned}$$

where P_A and P_P are the population proportions for OP0201 and placebo, respectively, for no bulging TM 4 days after the start of a 10-day treatment regimen.

The following sensitivity analyses will be done:

- PP analysis population
- Complete case (ie, mITT subjects who completed the Day 4 visit; see Section 13.3)
- Complete case with the endpoint defined as no bulging TM at the Day 4 visit and no recurrence of bulging TM (see Section 12.7) throughout the remainder of the study, assessed at the Day 28 visit. In this instance, "complete case" is equivalent to mITT subjects who completed the Day 28 visit.

No bulging TM assessed at the Day 12 and Day 28 visits are secondary endpoints.

Summaries and Analyses (see Section 13)

No bulging TM will be summarized and analyzed separately by visit using logistic regression. Summary tables will include frequencies and percentages of no bulging TM for each treatment group by visit and p-values for the differences. Crude rates of no bulging TM by treatment group and visit will be graphically displayed using bar charts.

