16. CHANGES FROM THE PROTOCOL

Protocol	Change
Primary efficacy analysis to be done using the	ITT population replaced by mITT population
ITT population defined as all randomized	which excludes the first 3 subjects dosed.
subjects.	
Subjects with missing data at the Day 4 Visit	Multiple imputation will be used for missing
will be considered as having bulging TM and	data for the primary efficacy analysis, with a
those with missing data at the Day 12 Visit	complete-case sensitivity analysis added.
will be considered as having MEE.	
GEE will be used for analyses of repeating	All binary endpoints will be analyzed separately
binary endpoints.	by visit using logistic regression.
Secondary efficacy endpoints, which included	Tympanogram findings will not be analyzed
"normal tympanogram," will be statistically	and will be reported as descriptive statistics
analyzed.	only.
Secondary efficacy endpoints will be	Complete-case analyses using the mITT
analyzed using the Safety population.	population will be done for secondary efficacy
	endpoints.

Confidential Page 28 of 35

REFERENCES

- 1. International Conference on Harmonisation of Technical Requirements for Registration of Pharmaceuticals for Human Use, ICH Harmonised Tripartite Guideline, Statistical Principles for Clinical Trials (E9), September 1998.
- 2. American Statistical Association (ASA). (2018) Ethical Guidelines for Statistical Practice. Prepared by the Committee on Professional Ethics, April 2018. http://www.amstat.org/ASA/Your-Career/Ethical-Guidelines-for-Statistical-Practice.aspx.
- 3. International Conference on Harmonisation of Technical Requirements for Registration of Pharmaceuticals for Human Use, ICH Harmonised Tripartite Guideline, Structure and Content of Clinical Study Reports (E3), November 1995.
- 4. International Conference on Harmonisation of Technical Requirements for Registration of Pharmaceuticals for Human Use, ICH Harmonised Tripartite Guideline, Good Clinical Practice (E6), April 1996.
- 5. International Conference on Harmonisation of Technical Requirements for Registration of Pharmaceuticals for Human Use, ICH Harmonised Tripartite Guideline, General Considerations for Clinical Trials (E8), July 1997.
- 6. International Conference on Harmonisation of Technical Requirements for Registration of Pharmaceuticals for Human Use, ICH Harmonised Tripartite Guideline, Statistical Principles for Clinical Trials (E9), September 1998.

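### The primary efficacy population drops three randomised and dosed children, and no efficacy comparison of all randomised children is kept alongside it

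*SAP*

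**What the plan says.** Protocol 9.3: "The intent-to-treat (ITT) population is defined as all randomized Participants and will be used to assess the primary efficacy endpoint family". Protocol 9.4.1 repeats this for the analysis of both endpoints.

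SAP Section 7 defines the replacement set as "Subjects who were randomized excluding the first 3 subjects dosed (subject numbers 1001, 1002 and 1003"), and gives the reason: "as there was a known device malfunction for these subjects". SAP Section 16 lists this openly as a departure from the protocol: "ITT population replaced by mITT population", "which excludes the first 3 subjects dosed".

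The rest of the SAP follows the reduced set:

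- SAP 12: "For the family of primary efficacy endpoints, summaries and analyses will be done using the mITT population unless otherwise noted". Secondary endpoints use complete cases within the same set.
- SAP 7, per-protocol population: "Subset of the mITT population with no protocol violations" that may have affected the primary endpoints.
- SAP 12.1: "Complete case (ie, mITT subjects who completed the Day 4 visit". SAP 12.2 has the matching rule for Day 12. In both sections the no-recurrence sensitivity analysis is limited to mITT children who completed Day 28.
- Appendix B: every efficacy table is labelled mITT, Per Protocol, Complete Case or Tympanogram Subset. The all-randomised label is used only for non-efficacy outputs such as disposition, deviations, baseline characteristics, medical history and prior medications.

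The three children were dosed, so they belong to the Safety population. Their otoscopy findings appear in the descriptive ear-examination tables and listing (SAP 11.4 and Appendix B), where no treatment test is planned.

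**The concern.** An all-randomised analysis protects the comparison from exclusions made after allocation. Here three children are removed after randomisation and dosing, and nothing in the efficacy plan shows the result with them included.

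The stated reason does not put them outside the question being asked. Protocol 6.1.1 describes the study treatment as a drug-device combination product. Protocol Appendix 4 lists treatment interrupted or compromised by device failure among its examples of incidents, and Protocol 8.4.6 has such events collected during the study. A failure of the delivery device is therefore something that can happen under the assigned treatment.

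The SAP also does not say when the exclusion was decided, by whom, or with what knowledge of treatment or outcome. It cites Protocol Amendment 3 (21 August 2019), which was issued during enrolment and still defined ITT as all randomised.

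At stake is whether a reader of the final report can check that the primary result does not depend on these three children. As planned, the report would contain no such check.

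**Working it through.** **1. The plan's own power figure.** Inputs from SAP Section 5: 70 per group, 10% dropout (70 × 0.9 = 63 per group), placebo rates 0.40 and 0.30, difference 0.25, two-sided Pearson chi-square, Hochberg. Power for one endpoint at two-sided 0.025 is Φ[(d − 2.241·se0)/se1], where se0 is the pooled and se1 the unpooled standard error.

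- Day 4, 0.40 v 0.65: se0 = √(0.525 × 0.475 × 2/63) = 0.0890; se1 = √((0.24 + 0.2275)/63) = 0.0861; power 72.1%.
- Day 12, 0.30 v 0.55: power 73.1%.
- At least one, treating the endpoints as independent: 1 − (1 − 0.721)(1 − 0.731) = 92.5%. The SAP states 93%, so the figure reproduces.

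**2. Power without the three.** Three of 140 is 2.1%. With 69 and 68 left, 10% dropout gives 62.1 and 61.2 per arm. Power is 71.1% and 72.1%, and at least one is 1 − (1 − 0.711)(1 − 0.721) = 91.9%. The loss is 0.6 of a percentage point.

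**3. Effect on a borderline result.** The unadjusted chi-square, the SAP's basis for power, stands in for the planned covariate-adjusted logistic regression with multiple imputation. For OP0201 38/70 v placebo 26/70: pooled rate 64/140 = 0.457; standard error √(0.457 × 0.543 × 2/70) = 0.0842; z = (0.543 − 0.371)/0.0842 = 2.04; p = 0.042.

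Now remove three children, split 2:1 or 1:2 between arms, in every response pattern:

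| Removed (OP0201 : placebo) | Responders among them (OP0201, placebo) | Remaining | p |
|---|---|---|---|
| 2:1 | 0, 0 | 38/68 v 26/69 | 0.033 |
| 2:1 | 0, 1 | 38/68 v 25/69 | 0.021 |
| 2:1 | 1, 0 | 37/68 v 26/69 | 0.050 |
| 2:1 | 1, 1 | 37/68 v 25/69 | 0.033 |
| 2:1 | 2, 0 | 36/68 v 26/69 | 0.073 |
| 2:1 | 2, 1 | 36/68 v 25/69 | 0.049 |
| 1:2 | 0, 0 | 38/69 v 26/68 | 0.048 |
| 1:2 | 0, 1 | 38/69 v 25/68 | 0.032 |
| 1:2 | 0, 2 | 38/69 v 24/68 | 0.020 |
| 1:2 | 1, 0 | 37/69 v 26/68 | 0.071 |
| 1:2 | 1, 1 | 37/69 v 25/68 | 0.048 |
| 1:2 | 1, 2 | 37/69 v 24/68 | 0.031 |

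Two of the 12 patterns fall below 0.025 and two rise above 0.05. (The 0.050 entry is 0.0495.) Crossing can also go against the drug: 42/70 v 28/70 (p=0.018) becomes 41/69 v 28/68 (p=0.033).

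The 2:1 and 1:2 splits are the only ones possible if the three share a randomisation block, because SAP 6.1 fixes the block size at 4. A 3:0 split needs children from more than one block, which the four strata allow. For example, 38/67 v 26/70 gives p=0.022.

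**4. When a crossing counts.** Under the Hochberg rule (SAP 13.4), an endpoint is held to 0.025 only when the other endpoint has p>0.05. Otherwise it is held to 0.05. If the other endpoint is already at or below 0.025, the trial is positive whatever this one does.

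**5. How often the trial verdict would change.** Simulation of the full two-endpoint rule, with the three removed 2:1 or 1:2 and assumed to respond at the placebo rate:

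- no effect: just under 2% of trials, roughly evenly in both directions, with familywise error staying near 5%;
- true difference 0.15 to 0.20: about 4 to 6%;
- design difference 0.25: about 2%.

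**The case against.** The strongest reply is that the exclusion is narrow, declared and based on a physical fault rather than on outcome. Treatment was undisclosed to the investigator, sponsor and vendors (SAP 6.2). Amendment 3 says the code was still blinded, and Protocol 9.4 has the SAP finalised before database lock. Both arms use the same spray regimen. The study is an exploratory Phase 2a, three children are 2% of the sample, and a borderline p-value from 140 children is fragile in any case. The three also stay in the safety ear-examination output and in the subject-level listings, so a determined reader could rebuild counts for all dosed children.

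Most of this stands, and it limits the point. Several stronger readings are tempting but unsupported:

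- **That the children were removed because of their results.** The documents give neither their outcomes nor the date of the decision. They show a gap in the record, not selective exclusion.
- **That the rule is applied unevenly.** This would need later malfunctions kept in the analysis, and none is documented.
- **That the exclusion decides the trial or favours OP0201.** The working shows movement both ways, and a changed verdict in only a small minority of trials.
- **That ITT must be restored as the primary set.** This can be argued either way in an exploratory trial with a known device fault, and the point does not depend on it.

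The reply does not supply the missing analysis. Disclosure tells the reader that the population changed, not whether the result did. The safety tables are descriptive, by ear and by treatment received, and carry no test.

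**Conclusion.** The point holds as a gap in the sensitivity analyses. The protocol's all-randomised population has been replaced, and no planned efficacy comparison includes the three children. The expected effect is small: power of about 92.5% becomes 91.9%, and the conclusion is unlikely to change. In a borderline case the exclusion can shift the p-value materially in either direction (0.042 to between 0.020 and 0.073 in the example), subject to the Hochberg condition above.

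These sizes rest on assumptions: the arms and outcomes of the three are not given, the arm splits and counts are illustrative, the chi-square replaces the planned model, and the verdict-change rates assume response at the placebo rate. The absence of an all-randomised efficacy analysis rests on none of them. It can be read directly from SAP 7, 12, 12.1, 12.2 and Appendix B.

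**What to change.** Add to SAP 12.1 and 12.2 a named sensitivity analysis of each primary endpoint in all randomised children, including 1001, 1002 and 1003, by randomised arm. Use the same logistic regression and multiple imputation as the primary analysis, so that only the population differs. Give each its own table in Appendix B. In SAP 7 or 16, state when the exclusion was decided, by whom, and whether treatment and outcome were concealed at that time.

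The cost is one extra model run and one table per endpoint, plus a short SAP edit. The all-randomised estimate may be slightly diluted by three children who may have received little drug. That is acceptable in a sensitivity analysis and can be noted beside the result.
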